4.3 Study Enrollment Procedures

Subject Selection: Before entering the study, all subjects undergo a diagnostic evaluation for 2-3 months to establish that they meet criteria for PMDD, as required by DSM-IV:

- A. In most menstrual cycles during the past year, five (or more) of the following symptoms were present for most of the time during the last week of the luteal phase, which began to remit within a few days after the onset of the menstrual flow, and were absent in the week post-menses, with at least one of the five symptoms being from among those numbered 1, 2, 3 or 4.
 1. markedly depressed mood, feelings of hopelessness, or self-deprecating thoughts
 2. marked anxiety, tension, feelings of being "keyed up" or "on edge"
 3. marked affective lability (e.g., feeling suddenly sad or tearful or increased sensitivity to rejection)
 4. persistent and marked anger or irritability or increased interpersonal conflicts
 5. decreased interest in usual activities (e.g., work, school, friends, hobbies)
 6. subjective sense of difficulty in concentrating
 7. lethargy, easy fatigability, or marked lack of energy
 8. marked change in appetite, overeating, or specific food cravings
 9. hypersomnia or insomnia
 10. a subjective sense of being overwhelmed or out of control
 11. other physical symptoms, such as breast tenderness or swelling, headaches, joint or muscle pain, a sensation of bloating, weight gain
- B. The disturbance markedly interferes with work or school or with usual social activities and relationships with others (e.g., avoidance of social activities, decreased productivity and efficiency at work or school).

- C. The disturbance is not merely an exacerbation of the symptoms of another disorder, such as major depression disorder, panic disorder, dysthymia disorder or a personality disorder (although it may be superimposed on any of these disorders.)
- D. Criteria A, B, and C must be confirmed by prospective daily ratings during at least two consecutive symptomatic cycles.

Note: Although the criteria for PMDD are in the main body of the text and formatted slightly differently in DSM-5, the diagnostic criteria for PMDD have not changed between DSM-IV and DSM-5. Thus, no alterations to the DSM-IV SCID criteria are needed to establish diagnosis.

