The potential risks include fatigue. Subjects will be encouraged to stay at home the day after wake therapy or, if driving, arrange alternative transportation. In previous studies of one night of total wake therapy in PMDD patients, subjects felt energized and wished to return to work or other daily activities. Previous studies also included two consecutive nights of partial wake therapy. We anticipate fewer problems in this study with only one night of partial wake therapy.

The following risk-management procedures will be used:

Depression, Anxiety, Suicidality, Mania:

To guard against adverse effects, all subjects will have a complete psychiatric history administered by a certified clinician. By monitoring mood twice daily and by providing weekly ratings by trained clinicians, we expect to detect any problems with mood before they become severe. Known bipolar patients are excluded to reduce the risk of mania occurring. Suicidal ideation will be monitored by the Clinical Rater at the time of HRSD administration. Patients are instructed to call the Rater, Study Coordinator, Research Associate or on-call psychiatrist if these symptoms occur. Suicidal ideation will be evaluated by both the Clinical rater and PI to determine the best course of action. A licensed psychiatrist will always be on-call to subjects should any psychiatric emergency arise. If needed, patients will be referred for appropriate treatment including inpatient hospitalization if warranted.

Urine Collections:

Trained staff will instruct participants in the proper method of urine collections.

Wake Therapy:

To ensure sufficient wakefulness after the wake therapy interventions, the patient is encouraged to stay at home, not drive or operate machinery and arrange for alternate transportation, for which they will be reimbursed. To avoid the induction of mania, bipolar patients are excluded.

Actiwatch:

Equipment will be checked regularly and its use by subjects overseen by specifically trained personnel to ensure maximum safety and comfort.

Pregnancy:

Subjects are warned not to rely on "time of the month" for contraception.

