7.3 Adverse Events and Serious Adverse Events

An adverse event (AE) is any untoward medical occurrence in a subject during participation in the clinical study or with use of the experimental agent being studied. An adverse finding can include a sign, symptom, abnormal assessment (laboratory test value, vital signs, electrocardiogram finding, etc.), or any combination of these.

A serious adverse event (SAE) is any adverse event that results in one or more of the following outcomes:

- Death

- A life-threatening event
- Inpatient hospitalization or prolongation of existing hospitalization
- A persistent or significant disability/incapacity
- A congenital anomaly or birth defect
- An important medical event based upon appropriate medical judgment

AEs will be categorized according to the likelihood that they are related to the study intervention as follows:

0 – Definitely unrelated:	AE is clearly not related to the investigational agent(s)
1 – Unlikely:	AE is doubtfully related to the investigational agent(s)
2 – Possibly related:	AE may be related to the investigational agent(s)
3 – Probably related:	AE is likely related to the investigational agent(s)
4 – Definitely related:	AE is clearly related to the investigational agent(s)

All AEs (and SAEs) will be recorded by the study coordinator, research associate or other staff member as they occur. Reports that include onset time, duration, severity, etc., will be sent to PI for review to determine actions to be taken, relatedness to study and monitoring of outcomes.

Mood ratings and side effects checklists will be utilized to assess treatment safety.

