9.5.2 Secondary Outcomes

- Effects of expectation, morningness/eveningness and seasonality on primary outcome measures:
Prior to entering the study, subjects will complete expectation forms measuring their expectation for change with the interventions (100 mm line from "much worse" to "much better") as well as Horne-Östberg scales to assess morningness and eveningness, as these variables may mediate or moderate primary outcome measures. To determine whether seasonality affects outcome, subjects will complete the Seasonal Pattern Assessment Questionnaire (SPAQ).
- Treatment-related changes from baseline (month 2) and 1-2 days post intervention (months 3,5) in reproductive hormones:
We will obtain overnight urinary samples for estradiol, progesterone, gonadotropins and prolactin (obtained at the same time of 6-SMT overnight collections in baseline and intervention months).
- Subjective visual analog scale-based global assessment of treatment effectiveness:

Following both treatment interventions, subjects will complete a visual analog scale-based global assessment of treatment effectiveness.

- Subjective assessment of side effects to treatment: collected 1-2 days post intervention (months 3,5)

Following each treatment interventions, subjects will complete an assessment of side effects using the Side Effects Checklist.

As delineated in our Data and Safety Monitoring Plan, the Independent Monitoring Committee will meet on an annual basis to review outcome data. The committee will be masked to a participant's intervention group assignment.

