15. SUPPLEMENTS/APPENDICES

I. Procedures Schedule

Consult Schedule of Evaluations (see section 6.1) for specific evaluations, forms and ratings associated with each time point listed below.

1. Screening:
 - a. Telephone screening to ensure potential participants meet eligibility criteria and to schedule initial in-office screening visit,
 - b. Screening Visit:
 - i. Patient signs Screening Consent
 - ii. Perform urine toxicology screening
 - iii. Complete Menstrual Assessment Questionnaire
 - iv. Record most recent start of menses (Cycle Day 1)
2. Evaluation Month 1
 - a. Evaluation week 1
 - i. Provide patient with binder that includes all required study forms, calendars, checklists and equipment/collection instructions needed in Evaluation Months 1 and 2
 - b. Evaluation week 2
 - c. Evaluation week 3
 - d. Evaluation week 4
3. Evaluation Month 2
 - a. Record Cycle Day 1 (patient will call Study Coordinator with date)
 - b. Evaluation week 5 – (Steps i – iv below must occur before Cycle Day 10):
 - i. Provide Clearblue® ovulation (luteinizing hormone surge-LHS) test kit
 - ii. Provide urine collection kit
 - iii. Provide Actiwatch Spectrum
 - iv. Provide instructions and demonstration of proper form completion, sample collection and equipment use
 - c. Evaluation week 6
 - d. Evaluation week 7
 - e. Evaluation week 8
 - f. The following steps are not categorized within the previous 4 evaluation weeks (5-8) as varying menstrual cycle times make it difficult to determine exactly when each of the following events will occur:
 - i. Menstrual Cycle Day 10 – commence testing for LHS (7 days of testing)
 - ii. Ovulation Day (LHS) – commence actigraphy recording (for 10 days)
 - iii. 8-9 Days after LHS (LHS+8 → LHS+9) – commence urine collection (30 hrs)
 - iv. LHS+11 – equipment, samples and forms are returned to lab
4. Treatment 1 (Month 3)

- a. Record Cycle Day 1 (patient will call Study Coordinator with date and to schedule pre-intervention in-office visit)
 - b. Pre-Intervention Visit – to be completed between cycle days 1 and 10:
 - i. Patient signs the Study Consent
 - ii. Patient is randomized to treatment
 - iii. Provide ovulation test kit
 - iv. Provide urine collection kit
 - v. Provide Actiwatch Spectrum
 - c. Menstrual Cycle Day 10 – commence testing for LHS (7 days of testing)
 - d. Ovulation Day (LHS) – commence actigraphy recording (for 10 days)
 - commence Wake Therapy (1 night)

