 - e. Day after LHS (LHS+1) – commence first light treatment (for 7 days)
 - f. LHS+8 → LHS+9 – commence urine collection (30 hrs)
 - g. LHS+11 – equipment, samples and forms are returned to lab
5. Washout (Month 4)
- a. Perform clinical ratings only
6. Treatment 2 (Month 5)
- a. Record CD1 (patient will call Study Coordinator with date and to schedule pre-intervention in-office visit)
 - b. Pre-Intervention Visit – to be completed between cycle days 1 and 10:
 - i. Provide ovulation test kit
 - ii. Provide urine collection kit
 - iii. Provide Actiwatch Spectrum
 - c. Menstrual Cycle Day 10 – commence testing for LHS (7 days of testing)
 - d. Ovulation Day (LHS) – commence actigraphy recording (for 10 days)
 - commence Wake Therapy (1 night)
 - e. LHS+1 – commence first light treatment (for 7 days)
 - f. LHS+8 → LHS+9 – commence urine collection (30 hrs)
 - g. LHS+11 – equipment, samples and forms are returned to lab
7. Final Visit (can be performed at time of item 6.g. above)
- a. Review side effects to treatment and subjective global assessment of treatment effectiveness.
8. Follow-up (luteal phase in the month following Treatment 2)
- a. Perform clinical ratings per telephone.

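### The side-effects checklist promised after each treatment is missing from the treatment-month procedures and is never given in an untreated luteal phase, so each arm's excess over PMDD background cannot be estimated from it

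*Combined protocol and SAP*

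**What the plan says.** Section 9.5.2 lists the outcome as "Subjective assessment of side effects to treatment: collected 1-2 days post intervention (months 3,5") and adds: "Following each treatment interventions, subjects will complete an assessment of side effects using the Side Effects Checklist". That is one form per treatment, two per woman. Section 7.3 gives the form a safety role: "Mood ratings and side effects checklists will be utilized to assess treatment safety". Section 7.4 requires a yearly report that includes how often treatment-related side effects occur and how severe they are.

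The procedural sections are less clear. Section 6.2.4 itemises the measures for Months 3 and 5, and its closing paragraph names the self-report forms completed during and after the intervention. The checklist is in neither. Section 6.2.6 adds the global effectiveness form at the final visit but not the checklist. Section 6.2 says who collects and scores checklists, but not when. Appendix I mentions side effects once, at the final visit after Treatment 2: "Review side effects to treatment and subjective global assessment of treatment effectiveness". The appendix also says: "Consult Schedule of Evaluations (see section 6.1) for specific evaluations, forms and ratings associated with each time point listed below".

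The checklist is absent from the Month 2 baseline list (6.2.2), the washout list (6.2.5) and the post-study telephone follow-up (6.2.6).

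**The concern.** Two separate matters are at stake.

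The first is timing. A coordinator working from 6.2.4 and Appendix I would find no instruction to give the form after Treatment 1. The first prompt about side effects would come at the final visit, after the woman has had both treatments.

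The second is the reference level. The effects that the plan anticipates are also symptoms of the disorder. Section 7.1 says of wake therapy: "The potential risks include fatigue". For light it names mild sleepiness and possible disruption of sleep onset. The PMDD criteria in section 4.3 include "lethargy, easy fatigability, or marked lack of energy" (item 7) and excessive or insufficient sleep (item 9). Every scheduled checklist falls in a treated luteal phase and there is no untreated arm. A woman who is tired in most luteal phases may report fatigue on the form whatever treatment she had. The yearly safety report and the secondary outcome would then give rates that mix the disorder with the treatment.

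**Working it through.** The plan gives no figure for this point, so there is none to reproduce. The check sets the sections side by side and adds date arithmetic.

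**Due date under 9.5.2.** The last light session is on LHS+7 (section 3). One to two days later is LHS+8 to LHS+9, the same window as the PSQI, the sleep-quality scale and the urine collection in 6.2.4.

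**Checklists per woman under each reading**

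| Section followed | After Treatment 1 | After Treatment 2 | Untreated luteal phase |
|---|---|---|---|
| 9.5.2 | 1 | 1 | 0 |
| 6.2.4 and 6.2.6 as itemised | 0 | 0 | 0 |
| Appendix I final-visit review alone | 0 | at most 1, covering both treatments | 0 |

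The section 6.1 grid is not used. In the copy reviewed its columns are broken: the urine row keeps a single mark although the text requires collections in Months 2, 3 and 5.

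**Delay for Treatment 1 if side effects were asked only at the final visit.** Inputs:
- cycle length 26 to 32 days (section 4.1);
- treatments two cycles apart (section 5.1);
- last light session LHS+7;
- final visit possible at LHS+11 of Month 5 (Appendix I, items 6.g and 7).

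Assume that the interval between successive LH surges equals the cycle length. Then:
- Delay = 2 × cycle length + (11 − 7).
- Shortest: 2 × 26 + 4 = 56 days. Longest: 2 × 32 + 4 = 68 days. This is about 8 to 10 weeks.
- With one anovulatory cycle between treatments (section 5.1 allows a repeat month): 3 × 26 + 4 = 82 to 3 × 32 + 4 = 100 days.
- For Treatment 2 the delay is 11 − 7 = 4 days.

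Under that reading the two arms would be recalled over very different periods. Under 9.5.2 the delay is 1 to 2 days for both.

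**What the planned checklists can estimate.** Suppose the 9.5.2 schedule is followed. For a given item, write the probability of a report in arm A as b + a, and in arm B as b + c. Here b is the report rate in an untreated luteal phase, and a and c are the excesses due to each treatment. The two checklists give b + a and b + c. Their difference, a − c, is free of b. Neither a nor c can be recovered without an estimate of b, and no scheduled checklist supplies one. A rate quoted for one arm overstates that arm's excess by b.

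**The case against.** A reader might infer that the plan contradicts itself outright, with Appendix I restricting the checklist to the final visit. The documents do not support that. Appendix I is not a list of forms. It refers to section 6.1 for those, names no mood scale under Months 3 or 5 either, and has this step in both treatment months: "LHS+11 – equipment, samples and forms are returned to lab". A final-visit review is compatible with looking back over checklists already completed. The gap lies in 6.2.4, which is an itemised list.

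A reader might also infer that side effects cannot be assigned to an arm. That does not follow. Section 9.5.2 gives one dated form per treatment. Section 7.3 has adverse events recorded as they occur, with onset time, duration and severity, and rated for relatedness. Attribution weakens only if staff follow the procedural sections instead of 9.5.2, and even then the dated event reports remain. Those reports do not replace a systematic checklist, but they are a real safeguard.

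On background symptoms, three replies have force:
- Each woman is assessed under both treatments in the same luteal window, so the contrast between arms largely balances PMDD symptoms. The balance is not complete. The trial's hypothesis is that one arm relieves symptoms more, and a checklist difference could then partly reflect efficacy.
- Sleep has Month 2 references (actigraphy, PSQI, sleep-quality scale), and HRSD, BDI, BAI and PGWI are taken in untreated cycles. These are partial references, and nothing in the plan links them to checklist items.
- The checklist's items and wording are not in the documents. It may ask the woman to attribute each symptom to treatment. So it cannot be stated that PMDD symptoms will be counted as side effects, only that they can be, and the amount cannot be given.

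**Conclusion.** The concern holds in limited form and is worth correcting. The procedural sections do not carry out the checklist schedule in 9.5.2. The consequence is conditional: a delay of 56 to 68 days for Treatment 1, or up to about 100, arises only if staff follow 6.2.4 and Appendix I. It rests on surge-to-surge intervals equal to cycle length and on a final visit at the earliest time that Appendix I allows.

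The missing untreated reference applies even when 9.5.2 is followed exactly. Each arm's excess over PMDD background cannot be estimated from the checklist, and absolute rates can be inflated by an amount the documents do not allow anyone to compute. The comparison between arms, which is the trial's main contrast, is much less affected.

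**What to change.** 1. In section 6.2.4 and in Appendix I, list the Side-Effects Checklist at LHS+8-9 of Months 3 and 5, to match 9.5.2, and confirm that the section 6.1 grid agrees. Keep the final-visit item as a review of forms already completed.
2. Add the same form once at Month 2 LHS+8-9 in section 6.2.2, when urine is already being collected. If the form asks for attribution to treatment, record presence and severity of each item separately so that the Month 2 answer has meaning.
3. In section 9.6, state that items new or worse than at Month 2 will be tabulated by treatment, beside the raw rates. The raw rates should stay because Month 2 is also a cycle on which women were selected for symptoms. A high Month 2 score could make the new-or-worse count too low.

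The cost is one extra form per woman, with the paperwork that brings, plus short wording changes. No visit is added and no treatment is altered.

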9.6 Data Analyses

Analysis will be performed on data from subjects qualified for participation in accordance to DSM-IV criteria for PMDD (see section 4.3 for criteria and symptoms) as confirmed prospectively by Daily Mood Ratings (DMR).

Mood and Other Ratings: In study month 3 (first treatment), month 4 (washout), month 5 (second treatment) and month 6 (follow-up), we will examine objective (HRSD, atypical, mania – to evaluate symptom severity) and subjective (Beck– to evaluate symptom severity, visual analogue scale-*DMR*) mood (including irritability and anxiety) and physical symptom ratings as a function of diagnosis and time of wake/light interventions.

6-SMT data processing and circadian analyses: From the 6-SMT concentration, urine volume, and the collection times, the 6-SMT excretion rate (ng/h) is computed for each collection interval (the interval between one voiding and the next). Circadian parameters then are computed from analyses of the full time series of 5-min intervals representing each overnight collection. The best-fitting 24-hour cosine curve (for an assumed period of 24 h) is estimated with a least-squares technique to yield the acrophase time (peak), amplitude (1/2 height) and mesor (mean excretion rate (ng/h)) of the fitted curve. To further describe changes in circadian phase and waveform, we use the actual ng/h curve to estimate the circadian timing of nocturnal 6-SMT onsets and offsets algebraically from upward (onset) and downward (offset) crossings of the cosine mesor.

Reproductive Hormones: Levels will be correlated with circadian measures and mood ratings to determine reproductive hormonal influences on circadian physiology and mood.

Daily Sleep Logs will be analyzed for rhythm stability (consistency of standard deviations of sleep onset and offset times from night to night), before vs. after the interventions.

Actiwatches: Activity and illumination will be examined to determine time-in-bed and any naps that occur during the day. Daily total sleep time, wake time, number of awakenings and distribution of lengths of awakenings for night and day separately in each 24 h period will be determined using the automated sleep-wake scoring algorithm and custom SAS procedures that we have developed.⁷⁰ Extended cosinor analyses⁷⁰ will be done to determine the mesor, amplitude and acrophase of activity and illumination and the f-statistic (with higher values representing more robust and synchronized rhythms that we expect to correlate with improved mood). The mean and maximum light intensities (in lux) and the number of minutes above 1,000 lux

also will be examined. Analyses then will be done comparing activity, sleep and light exposure between groups and time of light intervention with the light and activity summary variables as continuous covariates. Baseline pre-intervention values and post-intervention activity and illumination values also can be compared for a specific light pulse. These analyses will determine if the following variables predict the magnitude of treatment and phase-shift responses: 1) The timing of activity onset and offset, 2) The amplitude of activity at baseline, 3) The illumination levels at baseline.¹ For young adults, the Actiwatch is an accurate method for recording both the in-bed interval and for estimating the time asleep.⁷¹ Although presumably less accurate on a nightly basis than PSG, the Actiwatch is capable of several weeks of round-the clock recording, which would not be feasible with PSG either in the CTRI or at home.

General Approach to Data Handling and Statistical Analyses: Care will be taken to insure the confidentiality, complete recording, and accurate computerization of the data. Items will be subject to range and relational checks. Crosscheck programs will be used to provide a 100% check of data entry. Descriptive statistics will be calculated on all data items. Distributions, means, medians, standard deviations, ranges, skewness and kurtosis will be calculated for all measurements. Missing data values will be minimized by intensive training of the interviewers in techniques of clarifying answers and checking questionnaires while participants are on-site. When missing values are identified, several approaches such as rescheduling tests or interviews will be used to acquire the necessary data. Furthermore, missing data will be examined to assess randomness. We expect missing data to be randomly distributed and will impute appropriate values. Missing data (i.e. loss to follow-up) will be tested to determine if it is informative, and the methods developed by Diggle⁷² and Ridout⁷³ to test for completely random dropouts will be applied. All available data will be used in our data analysis without any need to estimate missing data (see below).

Specifically, data for hypothesis 1.A. will be analyzed using a Random Regression Model (RRM), a generalized linear model described by Gibbons et al.,⁷⁴ Hedeker et al.⁶⁹ and Laird.⁷⁵ The random effects method has several advantages over more traditional analytic approaches such as a change score, end-point or repeated measures analysis of variance. This method allows the inclusion of subjects with missing data or those who were terminated early in the study, without relying on data imputation procedures. This method provides an estimate of the individual variability around the population trend, the variability of the individual intercepts (baseline values) and slopes (changes across time), and the correlation between them. A fully saturated treatment by time model will be utilized for inference. Co-variance structure will be chosen based on Akaike's Information Criterion (AIC). Random treatment effects also will be evaluated for importance based on the model AIC. This plan allows for any group level effects to be incorporated into the model. Denominator degrees of freedom will be calculated using the Kenward-Roger small sample correction. All subjects will be included in the analyses, and we will not focus only on subjects who complete the study. Our methods for data analyses include all subjects with any valid data points in the analyses. Secondary analyses will be performed on data from completers. Type 1 error will be controlled by correcting the p-value per domain. For hypothesis 1.B, an individual's slope for each of the dependent variables listed above will be calculated and will be used for correlational analysis using the Pearson method. In addition, we will examine the number of responders. The operational definition of the criteria for

response on the mood measures, the HRSD, SIGH-SAD and the BDI, is a decrease of > 50% in the pre-treatment/baseline score, while the remission criterion will be a decline to a value < 8 on the SIGH-SAD and BDI as per Terman et al.⁴¹ We will compare percentages of PMDD subjects achieving the Terman criteria in groups receiving different interventions using Chi Square analysis. Results from Expectation Forms and Horne-Ostberg Scales will be examined in relation to the magnitude of mood change after interventions as assessed by mood ratings, the Psychological General Well-Being Index (PGWI), and side effects checklists. We also will examine the effect of diagnosis and light intervention on measures of subjective sleep quality as measured by the Pittsburgh Sleep Quality Index (PSQI), and differences between groups or intervention on outcome measures as a function of the phase-angle difference (PAD) between melatonin timing (acrophase, onset, offset) and sleep (onset, end-time, mid-sleep) measures. Data for hypothesis 1.C will be analyzed similar to hypothesis 1.B. Data for hypothesis 2.A will be analyzed similar to hypothesis 1.A using RRM. Data from LWT + AM BWL, however, will be used only. Data for hypothesis 2.B will be analyzed similar to hypothesis 1.B by using individual slope in the correlational analysis. Data for hypothesis 3.A will be analyzed similar to hypothesis 1.B, and for hypothesis 3.B, similar to hypothesis 1.A using only EWT +PM BWL treatment data.

